Subjects who have died without ICU admission during the study will be counted as requiring ICU admission for the analysis.

Number of ICU Days

The number of ICU days from Day 1 to Day 29 will be calculated based on the ICU admission and discharge dates recorded in the eCRF. The calculated number of ICU days will be compared between treatment groups using 2-sided Student's t-test. The 90% CI and p-value will be presented.

If the Student's t-test normality assumption is found to be clearly violated, a sensitivity analysis will be performed using a non-parametric Wilcoxon rank-sum test. The p-value from the test will be presented.

Subjects who died will be assigned as hospitalized in the ICU for the number of days remaining from the day of death to Day 29 for the analysis. Subjects who are alive and never admitted into the ICU will be included in the analysis with a value of zero ICU days.

Subjects who were at ICU at study completion will be assigned an ICU end date equal to the date of completion for the purpose of deriving number of ICU days.

Subjects requiring mechanical ventilation

Subject data pertaining to mechanical ventilation use will be recorded in the database.

The proportion of ITT subjects who were on mechanical ventilation from Day 1 to Day 29 within each treatment group will be analyzed and compared using the method described above for the analysis of subjects requiring ICU admission.

Subjects who have died without mechanical ventilation during the study will be counted as requiring mechanical ventilation for the analysis.

Number of days on mechanical ventilation

The number of days on mechanical ventilation from Day 1 through Day 29 will be calculated based on the start/stop dates of mechanical ventilation recorded in the eCRF. Number of days on mechanical ventilation will be compared between treatment groups using 2-sided Student's t-test. The 90% CI and p-value will be presented.

If the Student's t-test normality assumption is found to be clearly violated, a sensitivity analysis will be performed using a non-parametric Wilcoxon rank-sum test. The p-value from the test will be presented.

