Subjects who died will be assigned as being on mechanical ventilation for the number of days remaining to Day 29 for the analysis. Subjects who had mechanical ventilation ongoing at study completion will be assigned a mechanical ventilation end date equal to the date of study completion for the purpose of deriving duration of mechanical ventilation. Subjects who are alive and never

CONFIDENTIAL

placed on mechanical ventilation will be included in the analysis with a value of zero days on mechanical ventilation.

Mortality Rate through Day 29

Subject status (Alive/Death) will be recorded in the database. If the vital status of the subject is missing at the end of the study, then the subject will be excluded from the binomial analysis for the mortality rate. The subject will be included in the Kaplan-Meier (KM) analysis with right censoring at the date the subject was last known to be alive.

The mortality rate (proportion of ITT subjects who die) through Day 29 within each treatment group will be presented along with a two-sided exact (Clopper-Pearson) 90% confidence interval (CI).

The observed difference in the mortality rate between treatment groups along with the exact unconditional 90% CI for risk difference will be calculated. The null hypothesis will be tested using Fisher's exact method and the p-value will be reported.

If deemed appropriate, an alternative analysis will be performed in which the survival rates will be estimated using the KM method. The KM estimates along with 90% CIs and survival curves will be provided. Based on the KM estimates, the survival probabilities and associated 90% CIs on Days 15 and 29 will be reported; in addition, the 25%, 50% (median), and 75% percentiles of the survival time with associated 90% CIs will be provided, as data permit. The survival rates between treatment groups will be compared using Log-rank test and the p-value from Log-rank test will be presented.

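### ICU-day and ventilator-day counts do not score death as the worst outcome: a late death after no stay or a short one counts fewer days than a surviving long-stay subject

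*SAP*

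**What the plan says.** SAP 6.2 starts both counts from recorded dates, with no exception for subjects who die. For ICU: "The number of ICU days from Day 1 to Day 29 will be calculated based on the ICU admission and discharge dates recorded". Ventilator days are "calculated based on the start/stop dates of mechanical ventilation recorded in the eCRF".

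Four rules then complete the counts:

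- Deaths, ICU: "Subjects who died will be assigned as hospitalized in the ICU for the number of days remaining from the day of death" to Day 29.
- Deaths, ventilation: "Subjects who died will be assigned as being on mechanical ventilation for the number of days remaining to Day 29 for the analysis".
- Survivors without a stay: "Subjects who are alive and never admitted into the ICU will be included in the analysis with a value of zero ICU days". Ventilation has the same rule.
- Stays still open at the end: "Subjects who were at ICU at study completion will be assigned an ICU end date equal to the date of completion". Ventilation again has the same rule.

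Each count is compared between arms with a two-sided t-test. A Wilcoxon rank-sum test is a sensitivity analysis, run only if normality clearly fails. SAP section 4 sets the significance level at 10%, and SAP 2.2.2 defines both endpoints over Day 1 to Day 29.

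**The concern.** The rule for deaths exists so that dying does not shorten the count and pass for a good result. The days it assigns shrink as the death comes later, however, and no floor or worst value backs them up. A subject who dies near the end of follow-up after little or no ICU care can therefore score better than one who spent two weeks in ICU and recovered.

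The two binary endpoints in the same section count a death without ICU admission or without ventilation as requiring it, so the SAP evidently means death to be unfavourable. The day counts do not reliably achieve that. At stake is the direction of the treatment difference on these two endpoints.

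The SAP also leaves open whether the assigned days add to the recorded stay or replace it. Two programmers could derive different values for the same subject.

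**Working it through.** The documents give no expected value, standard deviation or power for either endpoint, so there is no planned figure to reproduce. The scoring rule is applied directly.

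**Inputs.** Duration is end date minus start date plus 1 (SAP 4.6). The horizon is Day 29 (SAP 2.2.2 and 6.2). There are 100 subjects per arm (SAP section 9). Stay dates, death days and five affected subjects per arm are illustrative assumptions. Five per 100 echoes the 5% mortality in the stopping rule (SAP section 8), which is not a planning value for these endpoints.

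**Formulas**, with a = admission day and d = day of death:

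- Survivor: discharge day − a + 1.
- Death, replacement reading: 29 − d + 1.
- Death, additive reading, in ICU from a until death: (d − a + 1) + (29 − d) = 30 − a. The day of death cancels out.
- Death never in ICU, either reading: 29 − d + 1.

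**Individual scores**

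| Subject | Replacement | Additive |
|---|---|---|
| Survivor, ICU Days 8 to 21 | 14 | 14 |
| Never in ICU, died Day 13 | 17 | 17 |
| Never in ICU, died Day 27 | 3 | 3 |
| ICU from Day 20, died Day 27 | 3 | 10 |
| ICU from Day 10, died Day 13 | 17 | 20 |
| ICU from Day 10, died Day 27 | 3 | 20 |

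A death never in ICU beats the 14-day survivor when 30 − d < 14, that is, from Day 17 on. On the additive reading, a death in ICU beats that survivor when 30 − a < 14, that is, when admission was on Day 17 or later.

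The ICU rule counts from the day of death. If that day is also the last day of the recorded stay, plain addition counts it twice and gives 21 instead of 20 for admission on Day 10. The ventilation rule does not say whether the day of death counts, so a Day 27 death off the ventilator could score 2 or 3.

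**Arm level**

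1. Five Day 27 deaths never in ICU (3 days each) against five survivors with 14 days, all others zero. Means: 15/100 = 0.15 and 70/100 = 0.70. Variances: (45 − 2.25)/99 = 0.432 and (980 − 49)/99 = 9.404. Standard error: √((0.432 + 9.404)/100) = 0.314. t = −0.55/0.314 = −1.75 on 198 degrees of freedom, p = 0.081. The arm with the deaths looks better at the 10% level.
2. The same survivors against five deaths admitted on Day 20, additive reading: 0.50 and 0.70, p = 0.60. With admission on Day 10: 1.00 and 0.70, p = 0.58, and the deaths are now the worse arm.
3. Five deaths in each arm, never in ICU, Day 27 against Day 13: 0.15 and 0.85, p = 0.066. If all were in ICU from Day 10 until death and the days add, both arms have mean 1.00.
4. Case 1 with every death scored 29: 145/100 = 1.45 and 0.70, p = 0.29. The direction is right. In case 3 both arms then have mean 1.45.

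**Window.** Protocol 7.14 allows the completion visit up to two days after Day 29. A subject in ICU from Day 10 and still there at a Day 31 visit scores 31 − 10 + 1 = 22 by the end-date rule, against 29 − 10 + 1 = 20 within the endpoint's own window.

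**The case against.** The strongest reply is that the additive reading is the more natural one, since counting starts from recorded dates for everyone. A reader might infer from the death rule that a death's score depends on its date alone, so that postponing any death looks like benefit. The documents do not support that: on the additive reading, someone in ICU or ventilated without a break until death scores the same whatever the date, and the same as a survivor admitted that day and still there on Day 29.

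A reader might also infer that a late death ranks among the best outcomes. It does not, because survivors who never needed ICU or ventilation score zero, below any death dated before Day 29.

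Death is also captured elsewhere. It scores 8, the worst value, on the primary scale, it counts against the arm in the binary endpoints, and mortality has its own test. In case 1, five deaths against none give a two-sided Fisher p of 2 × C(100,5)/C(200,5) = 2 × 75,287,520/2,535,650,040 = 0.059. That contradicts the ICU-day result and would be reported beside it.

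The reversal also needs several late deaths with little or no ICU time gathered in one arm. The documents give no expected event rate that would make this likely or unlikely. Finally, the Day 1 to Day 29 definition can itself be read as capping ongoing stays.

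All of this limits the reach of the point. The wrong ordering remains on both readings, and the SAP itself provides for deaths without ICU admission or ventilation, the kind most affected.

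**Conclusion.** The point holds in a bounded form. The rule misorders late deaths with no stay or a short one against surviving long-stay subjects, whichever way the days are combined. A later date lowers the score for deaths outside ICU or off the ventilator. It does so for every death only if the assigned days replace the recorded ones, which the SAP does not state.

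In the illustration the misordering is 3 days against 14, and it can turn the planned t-test towards the arm with more late deaths. That arm-level result rests on assumed events and shows what the rule permits. It is not a forecast.

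The window conflict is separate and small: at most two days per subject still in ICU or ventilated at completion.

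A reader might infer that the Wilcoxon test should become the main comparison. The figures do not require it: in case 1 it gives p = 0.94 both before and after deaths are rescored, because each arm has the same number of non-zero subjects.

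The impact is limited to two secondary endpoints in a study that SAP 4.5 calls exploratory. Even so, this is a stated rule that gives a wrong order, so it should be changed before unblinding.

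**What to change.** In SAP 6.2, for both day-count endpoints:

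- Assign every subject who dies through Day 29 the value 29, whatever the date of death and whatever stay came before. This also settles the add-or-replace question and the double count of the day of death.
- End a stay that is still open at the earlier of the completion date and Day 29.
- Keep the planned tests.

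The cost is a few sentences and one derivation per endpoint, with no new data. Each death will carry more weight in the arm mean (29 instead of 3 for a Day 27 death never in ICU). The endpoint also becomes openly a composite of days and death, which the table titles should state.

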4.6 Data Derivations and Transformations

The following derivations will be used in this study:

Study Day (Note: There is no day 0 in this study):

- Date of assessment date of 1st Study Drug administration + 1 for assessments done on or after date of 1st Study Drug administration
- Date of assessment date of 1st Study Drug administration for assessments done before date of 1st Study Drug administration

Baseline Observation: the last non-missing value prior to 1st Study Drug administration.

Duration:

- Duration in days = end date start date + 1
- Duration in minutes = end time in minutes start time in minutes

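### ICU-days and ventilation-days rules: a late death with little or no prior ICU or ventilator time scores fewer days than a long-stay survivor

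*SAP*

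**What the plan says.** SAP 2.2.2 lists ICU days and ventilation days as secondary efficacy endpoints, and SAP 6.2 gives the derivations.

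- **ICU days, base count:** "The number of ICU days from Day 1 to Day 29 will be calculated based on the ICU admission and discharge dates recorded".
- **ICU days, deaths:** "Subjects who died will be assigned as hospitalized in the ICU for the number of days remaining from the day of death to Day 29".
- **ICU days, survivors:** "Subjects who are alive and never admitted into the ICU will be included in the analysis with a value of zero ICU days". For those still in ICU at the end, "Subjects who were at ICU at study completion will be assigned an ICU end date equal to the date of completion".
- **Ventilation days:** these "will be calculated based on the start/stop dates of mechanical ventilation recorded in the eCRF". For deaths, "Subjects who died will be assigned as being on mechanical ventilation for the number of days remaining to Day 29 for the analysis".
- **Test:** "The calculated number of ICU days will be compared between treatment groups using 2-sided Student's t-test". A rank-sum test is the sensitivity analysis if normality is clearly violated. Ventilation days are tested in the same way.
- **Day counting (SAP 4.6):** "Duration in days = end date start date + 1" (the minus sign is lost in the text conversion).

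Elsewhere the plan treats death as the worst outcome. It scores 8, the top of the ordinal scale in SAP 6.1. In the yes/no ICU and ventilation endpoints of SAP 6.2, a death without ICU or ventilation counts as having required it.

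**The concern.** Crediting days after death has one evident purpose: to stop a death from looking like a short stay. The credit covers only the time left to Day 29, so it is small when death comes late. If the subject also had little or no earlier ICU or ventilator time, the total is small too, and the subject appears to have done better than someone who survived a long stay. With fewer days read as better, an arm with more deaths of this kind can show the more favourable mean.

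This departs from the plan's own ordering. A subject who dies on Day 29 without ICU counts as requiring ICU in the yes/no endpoint, yet may carry the same zero ICU days as a healthy survivor. The rank-sum test uses the same values, so it inherits the ordering.

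The wording is also incomplete. It does not say that remaining days are added to observed days, or whether the day of death belongs to the observed stay, the remaining days or both. SAP 4.1 calls for double programming, and two programmers could reasonably derive different values.

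**Working it through.** The documents give no expected ICU use, standard deviation or power for these endpoints, so there is no planned figure to reproduce. The event counts and dates below are assumptions. Inputs from the SAP are 100 subjects per arm (section 9), two-sided tests at 10% (section 4), 90% intervals, and zero days for survivors never in ICU (section 6.2).

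**Score for one subject.** Let a be the ICU admission day and d the day of death. With observed plus remaining days and the day of death counted once, a death in ICU after one continuous stay scores (d - a + 1) + (29 - d) = 30 - a, whatever the day of death. A death without ICU scores 29 - d, or 30 - d if the day of death counts.

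| Subject | Days scored |
|---|---|
| Survivor, ICU Days 5-24 | 20 |
| Survivor, ICU Days 10-29 | 20 |
| ICU from Day 10, dies in ICU Day 28 | 19 + 1 = 20 |
| ICU from Day 24, dies in ICU Day 27 | 4 + 2 = 6 |
| No ICU, dies Day 27 | 2 or 3 |
| No ICU, dies Day 29 | 0 or 1 |

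The third row ties with the survivor admitted on the same day. The last three fall well below the long-stay survivors.

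**Effect on the t-test.** Assume five active deaths on Day 26 without ICU, five placebo survivors in ICU on Days 8-24, and zero days for everyone else.

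- Each death scores 30 - 26 = 4 (day of death counted). Active mean = 5 x 4 / 100 = 0.20.
- Each placebo ICU survivor scores 24 - 8 + 1 = 17. Placebo mean = 5 x 17 / 100 = 0.85.
- Difference = 0.20 - 0.85 = -0.65 days.
- Variances: active (5 x 16 - 100 x 0.20²)/99 = 0.768; placebo (5 x 289 - 100 x 0.85²)/99 = 13.866.
- Standard error = √((0.768 + 13.866)/100) = 0.3825, so t = -1.70 on 198 df and p = 0.091.
- 90% CI = -0.65 ± 1.653 x 0.3825 = -1.28 to -0.02.

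This is significant at the SAP's 10% level in favour of the arm with all five deaths. Fisher's test on 5 v 0 deaths gives p = 0.059 in the opposite direction. If the day of death is not counted, each death scores 3, the difference is -0.70 and p = 0.066.

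**Same data with deaths at 29 days.** Active mean = 5 x 29 / 100 = 1.45. Difference = 1.45 - 0.85 = +0.60 (90% CI -0.62 to 1.82, p = 0.42). The rank-sum p is 0.94 under both scorings: with 95 zeros in each arm, re-ordering five values against five hardly moves it.

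**Where the problem stops.** Two further cases, again with five deaths v none in arms of 100, scored as observed plus remaining days:

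- All ten ICU subjects are admitted on Day 10; active subjects die on Day 26 and placebo subjects stay to Day 29. Every one scores 20, and the difference is 0.00.
- Active subjects are admitted on Day 22 and die on Day 26 (30 - 22 = 8 days); placebo subjects are in ICU on Days 8-24 (17 days). The difference is 0.40 - 0.85 = -0.45 (90% CI -1.13 to 0.23, p = 0.28).

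If the remaining days instead replaced the observed days, these two cases would give -0.80 (p = 0.075) and -0.65 (p = 0.091). The unstated choice therefore matters.

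**Day of death.** For ICU from Day 10 and death on Day 15, the observed stay is 6 days. Remaining days are 14 or 15, so the total is 20 or 21, while Days 10-29 are 20 days.

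**The case against.** A reader might infer that a death is credited with nothing but the days left to Day 29, so that any late death beats any long stay. The SAP does not support that. It derives the count from recorded dates and then deals with the days remaining, which reads most naturally as addition. On that reading a death in ICU never scores below a survivor with one continuous stay from the same admission day. That part of the objection stands and limits the problem to deaths with little or no earlier ICU or ventilator time.

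A reader might also infer that the day of death is certainly counted twice in the ICU endpoint. That is only one reading: days remaining after Day 15 are naturally 14, and SAP 4.6 is not explicitly applied to them. An extra day would also count against deaths, not for them. Nor do the documents say when deaths are expected, so it cannot be assumed that most would fall late. The ITT set can include subjects who were already positive on Day 1.

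Death is also captured elsewhere: in the primary scale, in the yes/no ICU and ventilation endpoints, and in a separate mortality analysis. SAP 4.5 calls the study exploratory and makes no multiplicity adjustment. The significant example needs five deaths, all late and outside the ICU, against five long-stay survivors. A milder one is far from significant: three active deaths on Day 25 without ICU (5 days each) plus three 14-day survivors, against six 14-day survivors on placebo, gives 0.57 v 0.84 days, p = 0.52. All of this stands and lowers the weight. It does not make the scoring of such deaths consistent with the rest of the plan.

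**Conclusion.** The point holds in limited form. As written, both rules rank a late death with little or no prior ICU or ventilator time as better than a long-stay survivor, against the plan's own ordering of outcomes. The t-test can then favour the arm with more deaths. The size shown, -0.65 days with p = 0.091 against +0.60 days when deaths take the worst value, rests on assumed event counts and dates and shows what is possible, not what is expected. The rank-sum test neither exposes nor corrects the problem in that example. Deaths after a long continuous stay are not under-scored if remaining days are added to observed days, but the SAP should say that they are. For secondary, unadjusted endpoints reported beside mortality, this is a cheap improvement and no threat to the trial's main conclusion.

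**What to change.** In SAP 6.2, replace the death sentence in both derivations with one rule: a subject who dies on or before Day 29 is assigned 29 days, whatever the date of death or earlier ICU or ventilator use. Twenty-nine is the most that a Day 1 to Day 29 count allows. Use the same value in the t-test and the rank-sum test. Show observed ICU and ventilation days among survivors descriptively, next to the mortality result. This also settles the add-or-replace question and the counting of the day of death.

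A worst rank for death, or ICU-free and ventilator-free days with death set to zero, would serve the same purpose. If the present rule is kept, state that remaining days are added to observed days and that the day of death counts once; that settles the derivation but leaves the ordering problem.

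The cost is two sentences and a small change to the derivation code before unblinding. The downside is that each death weighs more in the mean, so the endpoint becomes more death-led and overlaps more with mortality. That is the direction the plan already takes in its yes/no endpoints.

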6.3 Subgroup Analyses

Exploratory subgroup analyses of the primary efficacy endpoint by baseline characteristics, e.g. age group and gender, will be performed using the analysis method described in Section 6.1, if appropriate.

Additional analyses may be performed to gain a better understanding but would not replace analyses planned for primary and secondary efficacy endpoints.

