3.2 Treatment

3.2.1 Randomization Scheme and Treatment Arm Assignment

Subjects will be randomly assigned to receive PUL-042 Inhalation Solution or placebo in a 1:1 ratio. A central randomization system, the Medication Assignment Center (MAC; CTI Clinical Trial and Consulting Services), will be used for this study.

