4. GENERAL CONSIDERATIONS FOR DATA ANALYSIS

Unless otherwise specified, continuous variables will be summarized using descriptive statistics (n, mean, standard deviation, median, minimum, and maximum). Categorical variables will be summarized showing the number and percentage of subjects within each category.

Summary results will be provided for each treatment group. All tabulations will be based on pooled data across centers.

Unscheduled visits will be excluded from the summaries but will be included in the data listings.

All statistical tests will be two-sided and tested at the 10% level of significance.

Analyses will be performed using SAS for Windows statistical software, version 9.4 or higher (SAS, Cary, NC), except where other software may be deemed more appropriate.

CTI will perform all efficacy and safety analyses described in this SAP.

Subject data will be listed, sorted by treatment group and subject number. When applicable, listings will be additionally sorted by visit and assessment date/time.

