6. EFFICACY ANALYSES

Data on all efficacy endpoints will be listed and tabulated as appropriate.

6.1 **Primary Efficacy Endpoint and Analysis**

The primary efficacy analysis will be carried out on the ITT set.

The primary efficacy variable is the severity of COVID-19 as measured by the maximum difference from the baseline value in the Ordinal Scale for Clinical Improvement within 28 days from the start of experimental therapy. Randomized subjects are to be symptoms free and not known to be SARS-CoV-2 positive at baseline.

The Ordinal Scale for Clinical Improvement is a 9-point scale that measures disease severity at a given point in time. Notably, a score of 0 indicates that an individual is infection-free. The difference in scores obtained at different times provides a quantitative assessment of the incidence of infection and change in disease severity over that time interval.

The Ordinal Scale for Clinical Improvement to be used in this study is derived from a draft scale proposed by the World Health Organization^[1] for clinical improvement as presented below:

Descriptor	Score	
No clinical or virological evidence of infection	0	
Infected but no limitation of activities	1	
Limitation of activities	2	
Hospitalized not requiring oxygen therapy (SpO2 > 93% on room air)	3	
Oxygen by mask or nasal prongs	4	
Non-invasive ventilation or high-flow oxygen	5	
Intubation and mechanical ventilation	6	
Ventilation + additional organ support- pressors, RRT, ECMO	7	
Death	8	

Table 2 Ordinal Scale for Clinical Improvement (Derived from draft WHC)) scale)[1]
---	-------------

The null hypothesis is that there is no difference in mean maximum change in Ordinal scale from baseline through Day 29 between randomized treatment groups; H₀: $\Delta_t - \Delta_c = 0$. The alternative hypothesis is that the mean maximum change in Ordinal scale from baseline through Day 29 are different between the treatment groups; H₁: $\Delta_t - \Delta_c \neq 0$.

The change in severity of COVID-19 between the placebo- and actively-treated groups will be compared using an analysis of covariance (ANCOVA) model, including the maximum change in

Ordinal scale from baseline through Day 29 as a dependent variable, treatment group as a fixed effect, and baseline characteristics such as age as a covariate.

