From this model, the least-squares (LS) means and 90% CIs for each treatment group, the treatment difference in the LS means, the 90% CI for the difference, and the associated p-value will be presented.

If the data cannot support ANCOVA model assumption, a sensitivity analysis will be performed using proportional-odds cumulative logit model. The cumulative logits model will compare lower ordinal scales to higher ones, or equivalently, more favorable outcomes to less favorable ones. The model may be adjusted for baseline characteristics such as age, if appropriate. The estimated odds ratio and 95% CI will be presented.

The proportional odds assumption will be tested using a score test at the two-sided alpha level of 0.05. In the event that the proportional odds assumption is not satisfied, given the anti-conservative nature of the score test, the proportional odds model will still be used for the analysis, and the results will be presented along with the score test p-value to help put these results in context. If the proportion odds assumption is rejected or if the proportional odds model fails to converge, an alternative analysis using Cochran-Mantel-Haenszel (CMH) test will be performed to evaluate the association between the treatment groups and the maximum change in ordinal scale from baseline. The p-value for CMH row mean scores statistic will be reported.

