9. SAMPLE SIZE AND POWER CALCULATIONS

The trial size of 200 subjects (100 PUL-042 inhalation solution: 100 placebo) was chosen based on clinical considerations. The rates of infection to adequately estimate a sample size for a statistically significant result are unknown.

Enrolled subjects will be randomized with equal probability to receive blinded treatment consisting of either PUL-042 or placebo.

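### The exploratory subgroup analyses in SAP 6.3 reuse a model without a treatment-by-subgroup term, so no planned result addresses whether the effect differs between subgroups (minor).

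*SAP*

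**What the plan says.** SAP 6.3 plans exploratory subgroup analyses of the primary endpoint by baseline characteristics. Age group and gender are given as examples; there is no full list and no age cut-point. The analyses "will be performed using the analysis method described in Section 6.1, if appropriate". The same section allows further analyses, which would not replace the planned primary and secondary ones.

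The SAP 6.1 model has the maximum change in the ordinal scale as outcome, with "treatment group as a fixed effect, and baseline characteristics such as age as a covariate". From it, "the treatment difference in the LS means, the 90% CI for the difference, and the associated p-value will be presented". The fallbacks are a proportional-odds model and then a CMH test. None of the three is given a treatment-by-factor term.

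SAP 4 sets the level: "All statistical tests will be two-sided and tested at the 10% level of significance". SAP 4.5 makes no adjustment for multiple comparisons, because the study is exploratory.

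Neither document contains an interaction term, a heterogeneity test or a rule for reading subgroup results. Protocol Section 13 plans no subgroup analysis.

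**The concern.** A subgroup analysis asks whether the treatment effect differs between groups. The Section 6.1 model, fitted separately in each group, asks whether the effect differs from zero in that group. A significant result in one stratum and a non-significant one in the other does not show that the effects differ, because each stratum has only part of the sample and so less power than the whole trial.

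What is at stake is interpretation. Protocol Section 5 says the data will inform whether to advance to Phase 3. A table with a small p-value in one age group and a large one in the other invites the reading that only one group responds, even when the two estimates are compatible with the same effect.

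**Working it through.** The plan has no figure of its own to reproduce. SAP 9 states: "The trial size of 200 subjects (100 PUL-042 inhalation solution: 100 placebo) was chosen based on clinical considerations". It adds: "The rates of infection to adequately estimate a sample size for a statistically significant result are unknown". Power therefore has to be assumed and shown as a range.

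**Inputs from the SAP**
- Two-sided alpha 0.10 (SAP 4), critical value 1.645.
- 100 per arm (SAP 9), allocated 1:1 (SAP 3.2.1).

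**Assumptions**
- The same true effect in every subject.
- Two strata per factor: equal in the main case, 30/70 and 20/80 as variants.
- Overall power from 15% to 90%.
- Normal approximation.

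**Formulas**
- Let m be the mean of the overall z-statistic, chosen so that overall power = Φ(m − 1.645) + Φ(−m − 1.645).
- In a stratum holding a share f of the subjects, the mean of z is m√f. With equal strata this is m/√2.
- With stratum powers p₁ and p₂, P(exactly one significant) = p₁(1 − p₂) + p₂(1 − p₁). With equal strata this is 2p(1 − p).

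**Equal strata**

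| Overall power | m | m/√2 | p per stratum | 2p(1 − p) |
|---|---|---|---|---|
| 15% | 0.545 | 0.386 | 0.125 | 22% |
| 20% | 0.775 | 0.548 | 0.151 | 26% |
| 30% | 1.112 | 0.786 | 0.203 | 32% |
| 50% | 1.644 | 1.162 | 0.317 | 43% |
| 80% | 2.486 | 1.758 | 0.545 | 50% |
| 90% | 2.926 | 2.069 | 0.664 | 45% |

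For example, at 50% overall power, 2 × 0.317 × 0.683 = 0.433. At 80% overall power both strata are significant in only 0.545² = 30% of trials.

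**Unequal strata.** At 50%, 80% and 90% overall power the figure is 44%, 54% and 51% for a 30/70 split, and 46%, 59% and 59% for a 20/80 split.

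**Check on the ordinal scale.** The 0–8 score was simulated with 4,000 trials per scenario, 100 per arm, equal strata, an assumed severity distribution and t-tests. Assumed infection rates of 10% against 4%, 20% against 10%, and 30% against 15% (placebo against active) gave overall power of 42%, 50% and 66%. Exactly one stratum was significant in 41%, 45% and 48%, in line with the approximation.

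**Interaction test.** Under a uniform effect, a test of the treatment-by-factor term at two-sided 10% rejects in 10% of trials, whatever the overall power. Across the equal and 30/70 splits examined, at 50% to 90% overall power, only about 16% to 21% of trials with exactly one significant stratum also had a significant interaction.

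**Cost in power.** With equal strata, the interaction contrast has twice the standard error of the overall effect. At 80% overall power, an interaction as large as the overall effect has a z-mean of 2.486/2 = 1.243. Power is then Φ(1.243 − 1.645) + Φ(−1.243 − 1.645) ≈ 0.344 + 0.002, about 35%.

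**The case against.** Several points on the other side stand and limit the claim.

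- **Separate fits are not stated.** SAP 6.3 says the analyses are by baseline characteristics with the 6.1 method, if appropriate. Fitting that model in each stratum is the natural reading, but it remains a reading.
- **The analyses are exploratory.** No primary or secondary result depends on them, and the SAP nowhere says that significance in one stratum will be taken as a differing effect. The harm needs a reader's error.
- **The information is not lost.** With disjoint strata, a reader could difference the two LS-mean contrasts and combine their standard errors. What is missing is a planned contrast.
- **The size depends on assumed power.** For equal strata, 2p(1 − p) cannot exceed 50%, so the 43% and 50% figures lie near the maximum. At 15% to 30% overall power, which an unpowered Phase 2 trial may have, the figure is 22% to 32%; at 99% it is again about 22%.
- **Removing p-values is not enough.** A 90% CI that excludes zero is essentially the same decision as p < 0.10, so subgroup intervals show the same split unless the interaction result leads the interpretation.

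Two stronger readings are tempting. One is that a split will often appear whatever the drug does. With no effect at all, exactly one of two strata is significant in 2 × 0.10 × 0.90 = 18% of trials, but those are chance positives in either direction and not a uniform effect made to look selective. The other is that subgroup p-values will choose the Phase 3 population. The protocol speaks only of the feasibility of Phase 3, so that consequence is inferred.

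The possibility of additional analyses in SAP 6.3 does not answer the point: it commits to nothing, and an interaction test added after unblinding would not be pre-specified.

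**Conclusion.** The point holds as a minor one. SAP 6.3 names a method that does not address whether the effect differs between subgroups, and nothing elsewhere in the documents does. How often this would mislead cannot be fixed from the documents, which state no power, effect size, event rate or subgroup split. Over the assumed range of 15% to 90% overall power, a uniform effect gives one significant and one non-significant stratum in about 22% to 50% of trials with equal strata, and in up to 59% with a 20/80 split. An interaction test would signal a difference in 10%. The consequence is confined to the interpretation of exploratory subgroup results.

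**What to change.** In SAP 6.3, for each subgroup factor:

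- Fit the 6.1 model once in the full ITT set with treatment, factor and treatment-by-factor terms. If the proportional-odds model is used, put the same term in it.
- Report the interaction estimate with its 90% CI and p-value, as the sole basis for any claim that the effect differs.
- Show subgroup LS-mean differences with 90% CIs from that model as descriptive only, without within-subgroup p-values.
- State that a CI excluding zero in one subgroup but not in the other is not evidence of a difference, and that a non-significant interaction does not show a uniform effect.

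The CMH fallback, as planned, gives only a p-value and so cannot supply an interaction estimate. If it is the only model that can be run, the text should say that no between-subgroup claim will be made. The factors and age cut-points should be listed in the same edit, before unblinding.

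The cost is a few sentences and one model term per factor, with no new data and no change to the primary analysis. The downside is the interaction test's low power: about 35% for an interaction as large as the overall effect, at 80% overall power and equal strata, and lower if overall power is lower.
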